We will use the MRICron program's nonparametric lesion mapping (NPM) feature to complete the lesion symptom correlations^[106]. These data will be structured such that there is a binary classification at the voxel level (i.e., ±lesion) and continuous behavioral data (change score associated with the different outcome measures: PNT scores and scores on acquisition/generalization probes). Since these data are likely not to satisfy parametric statistical assumptions, we will use the NPM program's Brunner-Munzel nonparametric test to relate behavioral performance on each of the treatment-outcome predictors (change scores) to lesion distributions^[107-109]. We will apply a cluster threshold of 10 contiguous voxels and threshold for a false discovery rate of .05 in order to control for type I error while maintaining sufficient power to detect effects. We will also include voxels that have at least a 25% lesion overlap across patients. VLSM analyses will focus on four principal regions of interest (ROIs): left anterior cortex, left posterior cortex, left basal ganglia, and left hippocampus. Previous work (reviewed in section B.2 above) has shown that positive response to aphasia treatment is associated with intact left hippocampus and left basal ganglia. In addition, some previous work suggests that negative treatment response is associated with more intact left anterior cortex^[21], but other work suggests that greater recruitment of left anterior cortex is associated with positive treatment response^[23]. Additional work has also found that more intact left posterior cortex is associated with more positive treatment response^[23].

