Change scores from program entry to program exit and/or follow-up will be computed for primary and secondary study measures: weekly PNT scores and acquisition/generalization probes. These scores will be correlated with lesion extent using VLSM, with analysis focusing on the four ROIs identified above. These correlations will serve to test the hypotheses relevant to Specific Aim 1 above. As predicted by Hypothesis 1c and consistent with the preliminary findings from the PIRATE participants (see B.2.1 above), we anticipate that there will be a significant negative correlation between change scores and lesion extent in left basal ganglia and hippocampus. Greater damage to structures required for learning and memory function (hippocampus) and to structures which can control maladaptive activation of damaged left-hemisphere tissue (basal ganglia) will result in poorer treatment outcomes. Also as predicted by Hypothesis 1c and consistent with preliminary data by Parkinson and colleagues (see B.2.1), we anticipate that extent of left-anterior hemisphere lesion will be positively correlated with change scores. Greater damage to left anterior cortex will prompt greater recruitment of right hemisphere cortex or other non-lesioned left hemisphere cortex, resulting in more positive treatment outcomes^[20, 25]. Furthermore, we anticipate that extent of left posterior cortex will be associated with poorer treatment outcomes, given Fridriksson's findings^[23].

Additional exploratory analyses will be carried out to examine how these neuroanatomical factors predict performance for the different outcome measures. We anticipate that brain regions which are positively correlated with change scores for acquisition probes will not be positively correlated with change scores for generalization probes, given the behavioral^[9] and neuroimaging evidence^[20] that treatment response for treated and untreated items/behaviors leans on different cognitive and neural mechanisms. We do not have any a priori predictions regarding what brain regions may be correlated with change scores for generalization probes.

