To determine whether the proposed sample size will be sufficient to detect the lesion-behavioral correlations described above, a power analysis was carried out on the correlational data from Parkinson and colleagues^[21]. The correlation coefficients reported by Parkinson range from 0.65 to 0.85. Power analysis indicates that a sample size of 40 will provide power >0.99 for detecting effects of this magnitude and power of 0.80 for detecting correlations with r values of 0.38 or greater. Given the likely greater variability among the patients who participate in PIRATE, both in terms of their demographic characteristics and their language impairment profiles, we anticipate that any correlations between neuroanatomical markers and language performance and recovery may be somewhat weaker than those observed in the Parkinson and colleagues study^[21], which had a much more uniform sample. However, the projected sample size of 40 should be sufficient to detect weaker correlations than those observed by Parkinson and colleagues^[21].

If no significant correlations are found between the above ROIs and change scores for the outcome measures, we will perform additional VLSM analyses to examine the relationship between lesion site and extent and treatment response in subgroups of study participants. Since participants in this study will likely be more heterogeneous than those in previous studies, the data from the current study may be noisier due to greater inter-subject variability. To explore the effects of this variability on neural correlates of treatment response, participants will be divided by aphasia severity, their CAT T-scores, since different aphasia severities may be associated with different responses to treatment^[1]. Additional analyses may explore the lesion-treatment relationships found in different subgroups of veterans.

C.3.2 Dose-response analyses

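### The imaging power figure (0.80 at r = 0.38, N = 40) gives no alpha or sidedness, fits only one uncorrected correlation at one-sided 0.05, and is not the power of the planned FDR-controlled voxelwise test

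*Combined protocol and SAP*

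**What the plan says.** The power paragraph of C.3.1.3 takes correlations of 0.65 to 0.85 from a published lesion study. It reports that N = 40 gives power above 0.99 for effects of that size and "power of 0.80 for detecting correlations with r values of 0.38 or greater". It names no alpha, sidedness, formula or multiplicity allowance. It then expects that "any correlations between neuroanatomical markers and language performance and recovery may be somewhat weaker" than in that study, but concludes that "the projected sample size of 40 should be sufficient to detect weaker correlations" than the published ones. Section C.1 points to this calculation when it calls 40 enough for the neuroanatomical hypotheses.

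The analysis itself is described earlier in C.3.1.3. The data have a "binary classification at the voxel level", and each voxel is tested with the Brunner-Munzel rank test against change scores on the PNT and on the acquisition and generalization probes. The plan will apply a 10-voxel cluster threshold and "threshold for a false discovery rate of .05 in order to control for type I error". It will also "include voxels that have at least a 25% lesion overlap across patients". Interpretation focuses on four left-hemisphere regions. The predictions are directional, but no one-sided test is declared.

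**The concern.** A power figure without alpha and sidedness cannot be checked, and here the choice matters by about ten percentage points. The larger issue is that the figure is for one correlation, while the plan runs many voxelwise tests under an FDR threshold. No power is given for that procedure.

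N comes from program throughput and MRI exclusions (50 less 20%), so the sample size is not at stake. What is at stake is the meaning of a null imaging result. The section itself expects effects weaker than those published, and that is the range where the 0.38 figure would be relied on. A reader told that power was 0.80 at r = 0.38 could take a null as evidence against Hypothesis 1c when the planned test may have had much less power there. The same null also triggers further VLSM in severity subgroups, which are smaller still.

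**Working it through.** **Inputs.** N = 40 (C.1, C.3.1.3); r = 0.38 and r = 0.65 (C.3.1.3); FDR .05 and minimum 25% lesion overlap, i.e. 10 of 40 lesioned (C.3.1.3). Alpha and sidedness for the power figure are not stated, so both common conventions are tried.

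**Step 1: reproduce the stated figure.** Simple Fisher z: power = Φ(atanh(r)·√(N−3) − z). With atanh(0.38) = 0.4001 and √37 = 6.083, the product is 2.434.
- One-sided 0.05: Φ(2.434 − 1.645) = 0.785.
- Two-sided 0.05: Φ(2.434 − 1.960) = 0.682.

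The refined version uses the t-based critical r and a bias term: power = Φ([atanh(r) + r/(2(N−1)) − atanh(r_c)]·√(N−3)), where r_c = √(t²/(t² + N−2)) and r/(2(N−1)) = 0.38/78 = 0.0049.
- One-sided 0.05: t = 1.686, r_c = 0.264, atanh(r_c) = 0.270; Φ(0.1347 × 6.083) = 0.794.
- Two-sided 0.05: t = 2.024, r_c = 0.312, atanh(r_c) = 0.323; Φ(0.0822 × 6.083) = 0.691.

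| Convention | Fisher z | Refined | Simulation | Noncentral t |
|---|---|---|---|---|
| One-sided 0.05 (= two-sided 0.10) | 0.785 | 0.794 | 0.795 | 0.818 |
| Two-sided 0.05 | 0.682 | 0.691 | 0.693 | 0.716 |

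One-sided 0.10 gives 0.88 to 0.90. Of the conventions tried, only one-sided 0.05 (two-sided 0.10) returns 0.80 within two points. By the refined formula, the smallest r with 80% power is 0.383 at one-sided 0.05 and 0.427 at two-sided 0.05. At r = 0.65 power is 0.999 and 0.998, so the claim above 0.99 holds either way and does not show which convention was used.

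**Step 2: change to the planned test at one voxel.** Assume that 0.38 is already the point-biserial correlation between lesion status and change score. The mean shift in SD units is d = [r/√(1−r²)]/√(q(1−q)), with q the lesioned share: 0.4108/0.4330 = 0.949 for 10 v 30, and 0.4108/0.5 = 0.822 for 20 v 20. Simulated Brunner-Munzel power at p ≤ .05 is 0.68 to 0.70 two-sided and 0.78 to 0.80 one-sided. On this assumption the change of test costs little.

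If 0.38 instead describes a continuous lesion extent that is then dichotomised at 25% or 50% lesioned, power at p ≤ .05 is about 0.40 to 0.47 two-sided and 0.51 to 0.59 one-sided.

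**Step 3: add the FDR threshold.** The plan does not name the procedure. Under ordinary step-up FDR, the p cut-off is .05 times the share of tested voxels declared significant. That share is unknown; 50%, 25% and 10% are assumed. Per-voxel power on the point-biserial assumption at r = 0.38:

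| Share significant | Cut-off | Two-sided | One-sided |
|---|---|---|---|
| 50% | .025 | 0.58–0.61 | 0.68–0.70 |
| 25% | .0125 | 0.49–0.51 | 0.58–0.61 |
| 10% | .005 | 0.39–0.41 | 0.46–0.49 |

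Rejection under the null is slightly above nominal (0.056 and 0.053 at two-sided .05; 0.011 and 0.008 at .005), so these values are if anything a little high.

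**Step 4: larger effects, same assumptions, two-sided.** At r = 0.5, per-voxel power is 0.87–0.90, 0.81–0.85 and 0.71–0.77 at the three cut-offs. At r = 0.65 it is still about 0.97 or more at .005. If 0.65 is a continuous extent that is dichotomised, power at .005 is 0.68–0.80.

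**The case against.** The case for the plan has four parts.

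- **The arithmetic is right under a defensible convention.** The predictions are directional, and C.3.2 uses a 0.1 familywise rate for Aim 2, so one-sided 0.05 or two-sided 0.10 is not alien to this plan. This stands: the gap is one of reporting. A reader might infer a miscalculation, and the documents do not support that.
- **The sufficiency claim is modest.** C.3.1.3 says only that effects weaker than those published can be detected. For one correlation that is true at two-sided 0.05 down to r of about 0.43, and Step 4 shows good per-voxel power well below 0.65 on the point-biserial assumption. This also stands. The inference that N = 40 is generally too small does not follow.
- **Per-voxel power is not hypothesis-level power.** The hypotheses concern regions, and any qualifying cluster in a region counts, so regional power could exceed the values in Step 3. Those values must not be read as the power of the Aim 1 test. It remains true that no such power has been given.
- **The FDR cut-off need not be strict.** Adaptive FDR procedures can allow cut-offs above .05. This is why Step 3 is conditional on ordinary step-up FDR, and why the procedure needs naming.

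A further reading is tempting. Section B reports the published effects as partial correlations of opposite sign, each adjusted for the other region, while the VLSM names no covariate; a reader might infer that basal ganglia power must collapse. That depends on the correlation between the two lesion extents, which the documents do not give. Over assumed values from −0.3 to 0.7 the resulting power for a single two-sided 0.05 test runs from 1.0 down to 0.05, so it is not claimed as an error.

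**Conclusion.** The concern holds in limited form and should be fixed. The 0.80 at r = 0.38 belongs to one uncorrected correlation at one-sided 0.05 (0.79). At two-sided 0.05 the power is 0.69 and the detectable r is about 0.43. Confidence in this part is high, because it needs only N and r from the plan.

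The figure is also not the power of the specified voxelwise FDR analysis, whichever sidedness is meant. How far the planned test falls short at r = 0.38 can only be illustrated. Per voxel it is roughly 0.6 to 0.4 two-sided, or 0.7 to 0.46 one-sided, given the point-biserial assumption, step-up FDR and the assumed shares of significant voxels. It is lower if 0.38 refers to a dichotomised continuous extent. Cluster- or region-level power cannot be derived from the documents.

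The claim for r = 0.65 to 0.85 survives for a single correlation. The unsupported element is the 0.38 threshold and the reassurance that C.1 and C.3.1.3 draw from it.

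**What to change.** Restate the power sentence in C.3.1.3 along these lines: *For one zero-order correlation, N = 40 has power 0.69 at r = 0.38 and 0.80 at r of about 0.43 (two-sided 0.05). This is not the power of the FDR-controlled voxelwise test, which was not calculated.*

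In the same section, state the sidedness of the voxelwise test and name the FDR procedure. If one-sided tests are intended, declare this for each region and justify it for left anterior cortex, where the plan itself notes that "other work suggests that greater recruitment of left anterior cortex is associated with positive treatment response", contrary to the direction predicted under Hypothesis 1c. Limit the sufficiency statements in C.1 and C.3.1.3 to match.

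The cost is wording and a less favourable stated figure. N, the imaging protocol and the VLSM method do not change. A supporting region-level regression on lesion load could be added from the same masks, but it is optional: it would need a named atlas for the region boundaries and a multiplicity rule, and it would not repair the power statement.

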Second, six pairwise planned comparisons of scores across all seven consecutive measurement intervals will be carried out, using Bonferroni-corrected t-tests to maintain the familywise type-I error rate at 0.1. As predicted by Hypothesis 2a and consistent with the preliminary outcome data from PIRATE (see B.1.3 above), we anticipate that there will be a significant increase in both PNT score and acquisition/generalization probe performance for each additional one-week increment of treatment. We also predict non-significant changes between the initial evaluation and program entry and between program exit and follow-up.

In case a linear relationship is not found between time in treatment and outcome measures, additional analyses will be carried out examining the performance of different subsets of veterans. For example, veterans will be divided into groups based on their aphasia severity, since previous treatment findings have suggested that milder aphasia severity may be associated with less change on language-performance measures^[1]. Separate trend analyses will be carried out for the different severity groups, to examine whether different dose-response relationships may be observed for different aphasia groups.

In addition to these within-participant analyses examining dose-response relationships, a complementary set of between-participants analyses will be carried out, examining the effects of two versus four weeks of treatment for different randomly-selected groups of participants. It is standard practice in the dose-response literature to compare the response of groups exposed to different amounts of a therapeutic

agent, to see the incidence of positive or negative responses to the agent in the groups (e.g., frequency of remission or toxicity^[110]). These complementary between-participant analyses will simulate this comparison for the current study, providing an additional randomized-control measure of the effect of high dosage SFA on individuals with naming impairments. For these analyses, participants will be randomized to one of two groups. For half the participants, outcome measures (naming and PNT scores) will be sampled after two weeks' exposure, while for the other half, outcome measures will be sampled after the full four weeks of treatment. We anticipate that changes in study measures will be larger for the four-week group than for the two-week group.

C.3.3 Additional analyses of general language performance and connected speech

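### After a null lesion-mapping or trend result the plan retests within severity groups, with no interaction test and no correction for the second pass

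*Combined protocol and SAP*

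**What the plan says.** Section C.3.1.3 maps lesion status against change scores in an expected 40 patients, at a false discovery rate of .05, in four regions of interest (ROIs). It then adds a fallback, to be used only when the ROI results are null: "we will perform additional VLSM analyses to examine the relationship between lesion site and extent and treatment response in subgroups of study participants". The reason given is that a heterogeneous sample may be noisy and that response may differ by severity. The division is described only as "participants will be divided by aphasia severity, their CAT T-scores", and further subgroups, not defined, may follow.

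Section C.3.2 has a parallel fallback. If no linear relation between time in treatment and outcome is found, patients are grouped by severity (offered as an example) and "Separate trend analyses will be carried out for the different severity groups". The purpose given is to see whether dose-response differs between the groups. The sample here is the 50 completers expected in section C.1.

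The familywise rate of 0.1 in C.3.2 covers the pairwise t-tests only. No correction is stated for the trend tests, the severity retests or the repeated maps. Severity appears as a continuous adjuster only in the cognitive regressions of C.3.1.2, where it is optional.

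**The concern.** Three things go wrong together.

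- **Error rate.** The second pass runs only when the first has failed, so it adds chances of a positive finding on top of the nominal rate. With cut-points and number of groups left open, the added error has no stated limit.
- **Power.** Each retest uses a fraction of a sample that is already small. The plan justifies n=40 for the full imaging sample and gives no power for any part of it.
- **The question asked.** Whether dose-response differs by severity is a question about a difference between slopes. Separate tests of each slope against zero do not answer it.

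At stake is a claim that a lesion site predicts response, or that treatment amount matters, only in milder or only in more severe aphasia. Such a claim could affect who is offered treatment and how much of it.

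**Working it through.** **Inputs.** Imaging n=40 (C.1, C.3.1.3) and trend n=50 (C.1). Assumed, because the plan does not say: alpha 0.05, two equal severity groups, normal data, one ROI and one outcome. A single correlation test stands in for the voxelwise map.

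**1. The plan's own power figure.** C.3.1.3 claims "power of 0.80 for detecting correlations with r values of 0.38 or greater" at n=40. By Fisher's z, power = Φ(atanh(r)·√(n−3) − z_α), with atanh(0.38) = 0.400 and √37 = 6.083, so the product is 2.434.
- One-sided: Φ(2.434 − 1.645) = 0.785, close to the stated figure.
- Two-sided: Φ(2.434 − 1.960) = 0.68.

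The stated 0.80 is therefore reproduced only one-sided, and the plan does not give sidedness. For correlations that "range from 0.65 to 0.85", power exceeds 0.99 either way.

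**2. Detectable correlation after a split.** r = tanh((z_α + 0.842)/√(n−3)) for 80% power, two-sided:
- n=40: tanh(2.802/6.083) = 0.43
- n=20: tanh(2.802/4.123) = 0.59

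One-sided, the values are 0.39 and 0.54. At the plan's r=0.38, a half has one-sided power Φ(0.400·4.123 − 1.645) = 0.50 (0.55 by noncentral t), against the stated 0.80. For the trend, an effect with 80% power at n=50 has 49% in a half of 25 (two-sided one-sample t on patient slopes). All these figures assume the same effect in both groups.

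**3. False positives.** Simulated under no effect: a full-sample test at two-sided 0.05 and, if null, a 0.05 test in each group.

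| Analysis | Full sample only | Then two halves | Then three thirds |
|---|---|---|---|
| Correlation, n=40 | 5% | 12% | 17% |
| Trend, n=50 | 5% | 12% | not run |

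As a check, given a null full-sample correlation, at least one half is significant in 7.2% of cases, and 0.05 + 0.95 × 0.072 = 0.118.

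**4. What separate trend tests show when slopes are identical.** Simulated with n=50, two halves of 25, the same standardised slope (mean patient slope over its SD) and two-sided 0.05:

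| Slope | Full-sample trend null | One half significant, one not, given that null | Both events, all trials |
|---|---|---|---|
| 0.3 | 45% | 17% | 7.6% |
| 0.4 | 21% | 21% | 4.3% |
| 0.5 | 7% | 24% | 1.6% |

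A pattern that looks like a severity difference thus appears in 17 to 24% of triggered analyses when there is none.

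**5. Which full-sample model answers the question.** In one simulated example at n=40 with a pure lesion-by-severity interaction, power was 0.61 for the interaction term, 0.46 for at least one significant half, and 0.08 when severity was only an additive covariate. In a balanced check of the trend model, adding severity as a main effect left the estimated time slope unchanged. A covariate alone is therefore not enough in either section.

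**The case against.** These are fallbacks outside the main tests. C.3.1.3 presents its split as a way to explore variability, and C.3.2 names severity only as an example. The planned full-sample tests keep their power. If an effect sits at one severity level, splitting can help: in one simulated example a half had power 0.79 against 0.62 in the full sample.

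All of that stands, and it limits the point. It does not remove it, because neither section says that a positive subgroup result will be treated as hypothesis-generating only.

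A reader might infer more than the documents support:

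- *That the plan will compare which group is significant.* It does not say so. It simply provides no other between-group test.
- *That discordant halves would arise in 42 to 50% of trials.* That is the rate for two halves of 25 with identical slopes (0.3 to 0.5) when the null trigger is ignored. The plan splits only after a null, so the figures in step 4 apply.
- *That splitting costs more power than the severity noise it removes.* The documents give no correlation between severity and outcome, so this balance cannot be computed.
- *That splitting creates a problem for the Brunner-Munzel test in small groups.* At the rule of including "voxels that have at least a 25% lesion overlap across patients", a half could have 5 lesioned against 15 spared patients. But the unsplit minimum of 10 against 30 already shows excess rejection in simulation, and the size depends on software that cannot be examined here.

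**Conclusion.** The concern holds in a limited form. Both sections plan severity-group retests triggered by a null, with no interaction test and no correction. For one test with two equal groups, the error rate goes from 5% to about 12%. The detectable correlation in the imaging sample goes from 0.43 to 0.59 per half under a common effect. Separate trends do not address the stated purpose in C.3.2: with identical slopes, 17 to 24% of triggered analyses would show one significant and one non-significant half.

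These sizes rest on alpha 0.05 two-sided, equal groups and normal data, with single tests in place of the voxelwise procedure. More groups or outcomes would raise the error rate further. The matter should be put right, but it does not affect the validity of the primary full-sample tests.

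**What to change.** - **Dose-response (C.3.2).** Prespecify a continuous CAT-severity-by-linear-trend interaction in the full-sample mixed model, run whether or not the overall trend is significant.
- **Lesions (C.3.1.3).** For each ROI, prespecify a full-sample regression of change score on lesion load, continuous CAT mean modality T-score and their product, again whatever the first map shows. This needs a regression because the Brunner-Munzel test has no covariate term. State how the four interaction tests are corrected.
- **Do not residualise the change score alone on severity and then map the residuals.** This loses power when lesion and severity are correlated. In a simulation at n=40 with true partial r 0.43, power was 0.77, 0.68 and 0.47 at assumed lesion-severity correlations of 0.3, 0.5 and 0.7, against 0.80 with severity adjusted for on both sides. It also does not test whether the lesion effect differs by severity.
- **Subgroup maps and trends run after a null.** Report them as descriptive and hypothesis-generating only.
- **Severity measure.** Say which of the two pre-treatment CAT administrations is used.

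The cost is analysis wording and a small amount of extra analysis, with no new data or patients. The models assume a roughly linear severity effect, and power for an interaction at these sample sizes remains modest.

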studies delivering treatment at higher intensities exhibited larger effects. These findings are a significant part of the motivation for the intensive delivery schedule used in the PIRATE program at VAPHS. However, those studies which provided more intensive treatment have also provided more of it: the improvements seen in these studies could be due in part to greater treatment dosage^[7]. Furthermore, these studies have not systematically examined treatment amount, with most providing approximately 30 hours of treatment over a 2 week period^[29, 30, 55, 57, 81]. It is not known whether additional treatment on the same schedule would produce additional gains or would demonstrate diminishing returns.

Also unknown is how the amount of treatment received relates to acquisition and generalization in response to that treatment. As noted above, there is emerging evidence that the neural and cognitive mechanisms responsible for the two types of learning may be distinct^[9, 20]. In addition, there is evidence from the motor-learning literature suggesting that retention of trained behaviors and transfer to untrained behaviors may respond differently to different dosage levels^[82]. For non-speech motor learning, greater amounts of practice typically yield better retention of treated skills^[83, 84]. However, large amounts of practice may interfere with transfer to untreated skills, particularly under conditions of constant practice. Furthermore, the motor-learning literature suggests that the slope of performance curves for skill learning may vary widely even for a single behavior, depending on the choice of dependent measure^[85]. The relationship between treatment amount and mastery of treated skills or generalization to untreated skills thus remains unknown.

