Study measures will be subjected to two sets of analyses which test the dose-response hypotheses relevant to Specific Aim 2. These analyses will compare the PNT scores and acquisition and generalization probe scores across the 4 weeks of PIRATE treatment, to determine the dose-response relationship and to identify the points of largest change in response to treatment. The last of the three weekly naming probes will serve as a measure of weekly acquisition and generalization performance. This will ensure that performance on PNT and naming-probe measures may be directly compared, as they will be on the same schedule.

First, the data for the PNT scores and the acquisition/generalization probes will be analyzed with a multivariate mixed model with polynomial trend contrasts. To simplify interpretation, only time points 2 through 6 (program entry through program exit) will be included in the trend analyses. These trend analyses will first test whether there is a linear relationship between time in treatment and treatment response for study measures, as predicted by Hypothesis 2a. Second, they will test whether acquisition and generalization probes show additional curvilinear relationships to time in treatment, as predicted by Hypothesis 2b. We anticipate that there will be a positive linear trend between program entry and program exit for PNT scores and for acquisition and generalization probes. This finding would indicate that the four weeks of treatment results in significant score gains. We further predict that the trend for acquisition probes will also have a significant curvilinear (quadratic or higher-order) component, consistent with decelerating improvement across the four weeks of treatment. This finding would indicate that the largest gains for specifically treated skills/items occur early in treatment, with declining gains in later weeks. Finally, we predict that the generalization probes will also demonstrate a curvilinear relationship to time, due to accelerating improvement across the four week program. This finding would indicate that the largest gains for related but untreated items occur late in treatment, emerging later than the gains for specifically treated forms.

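### For the PNT, a significant linear trend shows overall gain but not linearity: no curvature test is named, and the other planned checks may be too weak to tell a plateau from a steady rise

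*Combined protocol and SAP*

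**What the plan says.** Section C.3.2 states that the PNT and probe scores "will be analyzed with a multivariate mixed model with polynomial trend contrasts", and that "only time points 2 through 6 (program entry through program exit) will be included in the trend analyses". That gives five weekly points.

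The first step, tied to Hypothesis 2a, covers every measure: "These trend analyses will first test whether there is a linear relationship between time in treatment and treatment response for study measures". The second step, tied to Hypothesis 2b, is narrower: "they will test whether acquisition and generalization probes show additional curvilinear relationships to time in treatment, as predicted by Hypothesis 2b". The PNT is not named there.

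A positive linear trend is predicted for the PNT and for both probe types. In the same paragraph, acquisition is expected to decelerate and generalization to accelerate. Of a positive trend the plan says: "This finding would indicate that the four weeks of treatment results in significant score gains".

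Two further analyses in C.3.2 include the PNT:
- Bonferroni-corrected weekly comparisons at a familywise rate of 0.1 ("six pairwise planned comparisons of scores across all seven consecutive measurement intervals will be carried out"), with a significant rise predicted in each treatment week under Hypothesis 2a.
- A between-participant comparison in which a random half is sampled after two weeks and the other half after four.

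The fallback reads: "In case a linear relationship is not found between time in treatment and outcome measures, additional analyses will be carried out". It looks at subsets of veterans, for example by aphasia severity. Section C.2.1 calls the PNT a secondary outcome measure for both aims.

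**The concern.** Section A.3 names the gap that the trial should fill: "It is not known whether additional treatment on the same schedule would produce additional gains or would demonstrate diminishing returns". A linear contrast does not fill it. It weighs late scores against early ones, so any curve that ends well above its start tends to give a positive value. The plan's own predictions show this: a decelerating curve, an accelerating curve and the PNT curve are all expected to pass the same test. Passing therefore cannot identify shape.

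For the probes, the curvature test covers this. For the PNT, the standardized naming measure, no curvature test is stated. Nor does C.3.2 say what counts as finding a linear relationship. If it means a significant linear contrast, a PNT plateau would not trigger the fallback, and the fallback examines subgroups, not shape. Weeks 3 and 4 could then be credited with a benefit they did not give.

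**Working it through.** The available text gives no power calculation or expected PNT gain for the dose-response analyses, so there is no stated figure to reproduce.

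**Inputs from the plan.** Five weekly points and a familywise rate of 0.1 over six comparisons (C.3.2); 50 completers (C.1); mean correlation between PNT forms 0.87 (C.2.2).

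**Assumptions.**
- Standard weights for equal spacing: linear −2, −1, 0, 1, 2; quadratic 2, −1, −2, −1, 2.
- PNT scaled to a between-person SD of 1, with error variance 1 − 0.87 = 0.13 per score.
- Between-person slope SD s of 0 to 0.1 per week.
- Total gain G of 0.25, 0.5 or 1.0 SD.
- Two-sided tests, 0.05 for contrasts and 0.1/6 = 0.0167 for each weekly test.

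**Step 1: contrast values.**

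| PNT curve, entry to week 4 | Linear | Quadratic |
|---|---|---|
| Straight: 0, 0.25G, 0.5G, 0.75G, G | 2.5G | 0 |
| Equal steps to G by week 2, then flat: 0, 0.5G, G, G, G | 2.5G | −1.5G |
| Same weekly rate, stops at week 2: 0, 0.25G, 0.5G, 0.5G, 0.5G | 1.25G | −0.75G |

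With unequal steps to G by week 2 the linear value is 2.2G (80% of the gain in week 1) or 2.8G (20% in week 1).

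**Step 2: power of the linear contrast.** SE = √[(10 × 0.13 + (10s)²)/50], which is 0.161 at s = 0 and 0.214 at s = 0.1. Power comes from the noncentral t with 49 df.
- G = 0.25: 0.82–0.97 for the straight rise and the same for the equal-total plateau.
- G = 0.5: above 0.99 for both.
- The same-rate curve with G = 0.5 gains only 0.25 SD in all, yet its contrast (1.25 × 0.5 = 0.625) is significant in about 82–97% of trials.

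**Step 3: the other planned PNT checks, under a true straight rise.**
- Weekly test: SE = √[(0.26 + s²)/50] = 0.072–0.073. At G = 0.5 the weekly gain is 0.125 and power is about 0.23–0.24. All four weeks are significant in about 0% of simulated trials (s = 0), and neither late week is significant in about 55%. At G = 1.0 each test has power 0.82–0.83.
- Two versus four weeks, 25 per group, change from entry: SE = √[((0.26 + (2s)²) + (0.26 + (4s)²))/25] = 0.144–0.170. At G = 0.5 the expected difference is 0.25 and power is 0.30–0.40. At G = 1.0 it is 0.82–0.93.

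**Step 4: contrasts available from the same model and data.**
- Within-participant week 4 minus week 2: SE = √[(0.26 + (2s)²)/50] = 0.072–0.077. Under a straight rise, power is 0.89–0.92 at G = 0.5 and 0.35–0.40 at G = 0.25. If the curve is flat after week 2, it rejects upward 2.5% of the time.
- Quadratic contrast: SE = √(14 × 0.13/50) = 0.191; a linear random slope drops out. Against the equal-total plateau, power is 0.97 at G = 0.5 and 0.49 at G = 0.25. Against the same-rate plateau at G = 0.5 it is also 0.49.

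**The case against.** There is a fair case for the plan, and it limits the point in four ways.

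**Equal contrast values.** A reader might infer that the contrast is the same whenever the PNT stops rising after week 2. It is not. Equality needs the same total gain, reached in equal steps by week 2. If the same weekly rate simply stops, the value is halved, and at G = 0.25 power falls from 0.82–0.97 to 0.30–0.48.

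**Hypothesis 2a has other tests.** A reader might infer that a PNT plateau would be reported as a linear dose-response. The documents do not support that. C.3.2 also ties Hypothesis 2a to a significant rise in every treatment week, and under a week-2 plateau each late weekly test shows a rise in only about 1% of trials. The two- versus four-week comparison then has an expected difference of zero. The plan's stated reading of a positive trend is itself limited to score gains.

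**The weekly pattern can be informative.** Under the equal-total plateau at G = 0.5, each of the first two weeks has power of 0.82–0.83 and the last two have no true gain. That differs visibly from a straight rise. The difficulty is with the reverse inference: with 0.23–0.24 power, a non-significant late week is also the usual result under a straight rise.

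**Scope.** The PNT is secondary, the probes do have a curvature test, and the PNT is in the polynomial model, so its quadratic term can be estimated. The wording of Hypotheses 2a and 2b is not in the available text, so whether 2a asserts strict linearity for the PNT cannot be confirmed.

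What stands is that no PNT shape test or rule for claiming linearity is stated, and that the checks in place are weak unless the gain is large.

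**Conclusion.** The concern holds in a limited form and should be fixed. A significant linear contrast cannot establish linearity or late-week benefit for the PNT, and a plateau could pass as a linear dose-response. The other PNT checks point the right way but have power of only about 0.23–0.24 per week and 0.30–0.40 between groups for a straight 0.5 SD gain. A significant trend with non-significant late weeks could then arise from either curve.

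The size depends on the gain, which the plan does not give: at 1.0 SD the existing checks are adequate. It also rests on n = 50, error variance 0.13 and slope SD 0–0.1. The equality at 2.5G is arithmetic and needs none of these, only the two curves specified.

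**What to change.** Amend C.3.2 as follows:

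1. State that the linear contrast tests overall gain from entry to exit.
2. For the PNT and each probe type, pre-specify the within-participant change from week 2 to week 4, with its confidence interval, as the test that further treatment adds benefit.
3. Name the quadratic contrast for the PNT and report it with its confidence interval.
4. State when linearity may be claimed. A significant linear contrast is not enough, and neither is a non-significant quadratic on its own.

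Both added contrasts are weak at a 0.25 SD gain (0.35–0.40 and 0.49), so the intervals should carry the interpretation. The cost is analysis-plan wording and two contrasts from a model already planned, with no new data or visits.
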